We now propose a phase I, dose escalation trial of cabozantinib in persons with HIV infection with advanced solid tumors. Given the broad range of anticancer activity observed in early phase studies, access to and evaluations of tolerability of this agent in persons with HIV infection is warranted so that such patients may be included on phase III trials of this agent. Certainly, effects on HIV/AIDS associated Kaposi sarcoma (example of a rare tumor) and hepatocellular carcinoma and non-small cell lung cancer (more common in persons with HIV-infection) would be of great clinical interest due to cabozantinib's effects on MET and VEGFR. Overexpression of HGF may have a role in angiogenesis of Kaposi sarcoma lesions (Naidu *et al.*, 1994) and evidence of VEGF/VEGFR2 and HGF/c-MET autocrine loop induction has been observed (Masood *et al.*, 1997; Maier *et al.*, 1996). *MET* mutations have been observed in gastric and liver cancer, small cell and non-small cell lung cancer, and metastases of head and neck squamous cell carcinoma, and gene amplifications in *c-MET* have also been observed in 15-25% of these tumors (Christensen *et al.*, 2005).

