- Clinically-significant gastrointestinal bleeding within 6 months before the first dose of study treatment
- Hemoptysis of  $\geq 0.5$  teaspoon (2.5 mL) of red blood within 3 months before the first dose of study treatment

- Any other signs indicative of pulmonary hemorrhage within 3 months before the first dose of study treatment

3.2.13 The participant has radiographic evidence of cavitating pulmonary lesion(s).

3.2.14 The participant has tumor invading or encasing any major blood vessels.

3.2.15 The participant has uncontrolled, significant intercurrent or recent illness including, but not limited to, the following conditions:

1. Cardiovascular disorders including:
  - a) Congestive heart failure (CHF): New York Heart Association (NYHA) Class III (moderate) or Class IV (severe) at the time of screening
  - b) Concurrent uncontrolled hypertension defined as sustained BP  $> 140$  mm Hg systolic, or  $> 90$  mm Hg diastolic despite optimal antihypertensive treatment within 7 days of the first dose of study treatment
  - c) Any history of congenital long QT syndrome
  - d) Any of the following within 6 months before the first dose of study treatment:
    - Unstable angina pectoris
    - Clinically-significant cardiac arrhythmias
    - Stroke (including TIA, or other ischemic event)
    - Myocardial infarction
    - Thromboembolic event requiring therapeutic anticoagulation (Note: participants with a venous filter (e.g. vena cava filter) are not eligible for this study)
2. Gastrointestinal disorders particularly those associated with a high risk of perforation or fistula formation including:
  - a) Any of the following within 28 days before the first dose of study treatment
    - Active peptic ulcer disease,
    - Inflammatory bowel disease (including ulcerative colitis and Crohn's disease), diverticulitis, cholecystitis, symptomatic cholangitis or appendicitis
    - Malabsorption syndrome
  - b) Any of the following within 6 months before the first dose of study treatment:
    - Abdominal fistula
    - Gastrointestinal perforation
    - Bowel obstruction or gastric outlet obstruction
    - Intra-abdominal abscess. Note: Complete resolution of an intra-abdominal abscess must be confirmed prior to initiating treatment with cabozantinib even if the abscess occurred more than 6 months before

the first dose of study treatment.

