## **4.0 REGISTRATION PROCEDURES**

### **4.1 General Guidelines**

Sites must have this protocol approved by their Institutional Review Boards (IRB) and be registered for study participation with the AMC Operations and Data Management Center (ODMC) before they may enroll participants.

After it has been determined, that the participant is eligible and an informed consent has been signed by the participant, the participant must be registered on-line via the AMC AdvantageEDCSM Internet Data Entry System (AdvantageEDC). Enrollment and data collection will occur via the AMC Internet Data Entry System.

The participating site will ensure a participant meets all eligibility criteria prior to completing the protocol-specific eligibility checklist in AdvantageEDC for enrollment. Participants will be enrolled on-line via AdvantageEDC no more than 1 week prior to the initiation of treatment (enrollment 1 day prior to or on the day of treatment is strongly encouraged). Once the eligibility checklist is submitted a system-generated confirmation email will be sent to the enroller upon successful completion of the participant enrollment. If the on-line system is inaccessible, the site should notify the AMC ODMC (via email at [[contact]](mailto:[contact]) or via phone at [contact]) for further instructions.

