#### 6.1.10 Guidelines for the prevention of hemorrhagic events

Hemorrhagic events have been reported with approved drugs that inhibit VEGF pathways as well as with cabozantinib. As preventive measures, participants should be evaluated for potential bleeding risk factors prior to initiating cabozantinib treatment and monitored for bleeding events with serial complete blood counts and physical examination while on study. Risk factors for hemorrhagic events may include (but may not be limited to) the following:

1. Tumor lesions with cavitations or tumor lesions that invade, encase, or abut major blood vessels. The anatomic location and characteristics of primary tumors or metastases as well as the medical history should be carefully reviewed in the selection of participants for treatment with cabozantinib.
2. Recent or concurrent radiation to the thoracic cavity.
3. Active peptic ulcer disease, ulcerative colitis, and other inflammatory GI diseases.
4. Underlying medical conditions that affect normal hemostasis (e.g., deficiencies in clotting factors and/or platelet function, or thrombocytopenia).
5. Concomitant medication with anticoagulants or other drugs that affect normal hemostasis.
6. History of clinically significant hemoptysis.

Based on the described predisposing risk factors for hemoptysis, many studies with antiangiogenic drugs exclude participants with non-small cell lung cancer (NSCLC) and squamous cell differentiation. Although enrollment of participants with NSCLC with squamous cell differentiation has been allowed on cabozantinib studies, cabozantinib studies exclude NSCLC participants with any of the following: tumors abutting, encasing, or invading a major blood vessel; cavitating lesions; history of clinically significant hemoptysis; or recent radiation therapy to the thoracic cavity including brachytherapy unless radiation therapy targets bone metastasis.

Cabozantinib should be discontinued in participants with serious and life-threatening bleeding events or recent hemoptysis ( $\geq 0.5$  teaspoon (2.5mL) of red blood). Treatment with cabozantinib should be interrupted if less severe forms of clinically significant hemorrhage occur and may be restarted after the cause of hemorrhage has been identified and the risk of bleeding has subsided at a dose agreed to by the Study Chair and the investigator. Therapy of bleeding events should include supportive care and standard medical interventions.

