Furthermore, participants who develop tumors abutting, encasing, or invading a major blood vessel or who develop cavitation of their pulmonary tumors while on study treatment must be discontinued from cabozantinib treatment.

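### No entry criterion covers an NSCLC tumour that abuts a major blood vessel, although Section 6.1.10 says cabozantinib studies exclude such participants

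*Combined protocol and SAP*

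**What the plan says.** **Entry.** Exclusion 3.2.14 is "The participant has tumor invading or encasing any major blood vessels". It is not restricted by tumour type. Section 4.1 makes the eligibility criteria the gate to enrolment: "The participating site will ensure a participant meets all eligibility criteria prior to completing the protocol-specific eligibility checklist in AdvantageEDC for enrollment".

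**Haemorrhage guidance.** Section 6.1.10 refers to abutment three times.

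- As a risk factor. It says that "participants should be evaluated for potential bleeding risk factors prior to initiating cabozantinib treatment". The first factor listed is "Tumor lesions with cavitations or tumor lesions that invade, encase, or abut major blood vessels", and tumour location and medical history "should be carefully reviewed in the selection of participants for treatment with cabozantinib".
- In a description of practice in NSCLC. Squamous NSCLC has been allowed on cabozantinib studies, but "cabozantinib studies exclude NSCLC participants with any of the following: tumors abutting, encasing, or invading a major blood vessel". The same sentence goes on to cavitating lesions, past significant haemoptysis and recent thoracic radiation.
- In a stopping rule. Treatment must end for "participants who develop tumors abutting, encasing, or invading a major blood vessel or who develop cavitation of their pulmonary tumors".

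**Imaging.** Section 9.1.10 requires a baseline CT within 4 weeks of starting therapy (Kaposi sarcoma excepted). Section 9.2.8 repeats it every 8 weeks for solid tumours.

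**The concern.** Section 6.1.10 puts abutment beside encasement and invasion each time it lists forms of vessel involvement. The entry criterion keeps the last two and omits the first. A site screening an NSCLC participant with an abutting tumour therefore gets two messages. The eligibility criteria admit the participant. The safety section says that studies of this drug exclude such a participant. Nothing in the protocol says which should prevail, or why abutment is treated differently at entry.

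The case is not remote. Section 2.5 says that "hepatocellular carcinoma and non-small cell lung cancer (more common in persons with HIV-infection) would be of great clinical interest", and Section 2.6.3 expects people with lung cancer to take part. Fatal bleeding on the drug is documented: Section 2.4 lists 15 treatment-related grade 5 events, of which five were haemorrhages (two gastrointestinal, one intracranial, one haemoptysis, one presumed haemoptysis). The documents do not connect any of these to vessel abutment.

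What is at stake is the safety of individual participants and consistent selection across sites. Two investigators could decide differently on the same scan and both comply with the protocol.

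**Working it through.** No arithmetic beyond a count applies. The check compares each condition in the 6.1.10 NSCLC sentence with all of Sections 3.1 and 3.2.

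| Condition in 6.1.10 (NSCLC) | Nearest entry criterion | Match |
|---|---|---|
| Tumour encasing a major vessel | 3.2.14, all tumour types | Full |
| Tumour invading a major vessel | 3.2.14, all tumour types | Full |
| Cavitating lesions | 3.2.13, pulmonary lesions only | Partial |
| History of clinically significant haemoptysis | 3.2.12, at least 2.5 mL of red blood, or other signs of pulmonary haemorrhage, within 3 months | Partial |
| Recent thoracic radiation | 3.1.1, completed at least 3 months before registration | Partial |
| Tumour abutting a major vessel | None | None |

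Count: 2 full + 3 partial + 1 with no counterpart = 6 conditions. The line between full and partial is a judgement, and a lenient reader could call all five matched conditions covered. The last row does not depend on that judgement: no criterion from 3.1.1 to 3.2.19 mentions abutment, and none is specific to NSCLC.

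Next, follow an NSCLC participant whose tumour abuts a major vessel without encasing or invading it.

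1. Exclusion 3.2.14 does not apply.
2. The participant must still meet the other bleeding-related criteria:
   - platelets of at least 100,000/mcL (3.1.6);
   - PT/INR and PTT below 1.3 times the upper limit of normal (3.2.8);
   - no therapeutic anticoagulation or antiplatelet treatment (3.2.9);
   - no recent bleeding as defined in 3.2.12;
   - no cavitating pulmonary lesion (3.2.13);
   - the 3-month gap after thoracic radiation (3.1.1).
3. None of these looks at contact between tumour and vessel. If they are met, abutment is considered only in the 6.1.10 selection review, which asks for care but gives no rule for deciding.
4. Once on treatment, the stopping rule covers contact that develops. Read literally, it does not reach contact already present at entry. One participant may start and continue with an abutting tumour, while another who acquires the same contact must stop.

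**The case against.** The strongest reply is that the 6.1.10 sentence is not a rule of this trial. It reports what cabozantinib studies do in general, in a section on managing adverse events. Eligibility is set by Section 3, which plainly does not exclude abutment. Nor was Section 3 written as a copy of that sentence, since three other conditions are carried over with different limits. On this view the protocol has a sensible two-tier scheme: encasement or invasion is an absolute bar, and abutment is judged case by case under 6.1.10.

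Much of this stands. The sentence is descriptive, and the documents do not show whether the omission from 3.2.14 was deliberate. The two-tier reading is coherent for tumours other than NSCLC. It does not work for NSCLC, because there 6.1.10 describes exclusion for abutment and not case-by-case review. The other differences concern thresholds or time windows for conditions that Section 3 does address. Abutment is the one it leaves out.

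Three stronger readings are tempting, and the documents do not support them.

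- *That enrolling such a participant breaches the protocol.* It does not, because the 6.1.10 sentence imposes no entry requirement on this trial.
- *That only the investigator's review stands between the participant and treatment.* The criteria in step 2 of the working still apply. On study, 6.1.10 adds serial blood counts and examinations, and directs that the drug be stopped for serious or life-threatening bleeding or for haemoptysis of 2.5 mL or more.
- *That the stopping rule contradicts 3.2.14.* It concerns contact that develops on treatment. New contact is a change in disease, so stopping for it does not by itself imply that contact present at baseline must be barred.

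The objection that no harm has been quantified is also correct, and it limits how strongly the point can be put.

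**Conclusion.** The point holds as an internal inconsistency on a safety criterion. For NSCLC, Section 6.1.10 describes exclusion for an abutting tumour and the entry criteria do not provide it. An NSCLC participant with such a tumour who meets the other bleeding-related criteria can be enrolled, with the abutment left to a review that binds no one.

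Its size in participants or events cannot be given. The documents do not say how many NSCLC participants would have an abutting tumour, or how much abutment adds to bleeding risk. All that can be counted is wording: one of six conditions has no counterpart in Section 3. That count does not measure harm. A reader might also infer an effect on the trial's conclusions, but nothing here changes the DLT definition, the escalation rules, the MTD determination, the sample size or any analysis.

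The conclusion rests on reading 3.2.14 literally, so that encasing does not include abutting. Section 6.1.10 supports this by listing the terms separately. Correcting the gap is a worthwhile and inexpensive improvement. It is not evidence of a serious design fault.

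**What to change.** Amend 3.2.14 to exclude tumour that invades or encases any major blood vessel or, in NSCLC, abuts one. Read this from the baseline CT in 9.1.10, and leave abutment in other tumour types to the existing 6.1.10 review.

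The change is a few words and needs no new procedure, provided the baseline CT covers the chest. Section 9.1.10 asks for CT of measurable disease without naming a region, but chest coverage can be expected in NSCLC. Abutting would be left undefined, as encasing and invading already are, so some differences in reading scans would remain. The main downside is possibly a few more NSCLC screen failures in a trial that expects to accrue 1 to 2 participants per month.

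Stating in 6.1.10 that baseline abutment is acceptable in NSCLC would also remove the inconsistency, but with no gain in safety, so amending 3.2.14 is preferred.

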### 3.3 Inclusion of Women and Minorities

Both men and women of all races and ethnic groups are eligible for this trial.

ACCRUAL TARGETS					
	Sex/Gender				
	Females	+	Males	=	Total
Ethnic Category					
Hispanic or Latino	3	+	8	=	11
Not Hispanic or Latino	9	+	22	=	31
Ethnic Category: Total of all participants	12 (A1)	+	30 (B1)	=	42 (C1)
Racial Category					
American Indian or Alaskan Native	0	+	1	=	1
Asian	0	+	2	=	2
Black or African American	8	+	16	=	24
Native Hawaiian or other Pacific Islander	0	+	1	=	1
White	4	+	10	=	14
Racial Category: Total of all participants	12 (A2)	+	30 (B2)	=	42 (C2)

(A1 = A2)

(B1 = B2)

(C1 = C2)

## **4.0 REGISTRATION PROCEDURES**

### **4.1 General Guidelines**

Sites must have this protocol approved by their Institutional Review Boards (IRB) and be registered for study participation with the AMC Operations and Data Management Center (ODMC) before they may enroll participants.

After it has been determined, that the participant is eligible and an informed consent has been signed by the participant, the participant must be registered on-line via the AMC AdvantageEDCSM Internet Data Entry System (AdvantageEDC). Enrollment and data collection will occur via the AMC Internet Data Entry System.

The participating site will ensure a participant meets all eligibility criteria prior to completing the protocol-specific eligibility checklist in AdvantageEDC for enrollment. Participants will be enrolled on-line via AdvantageEDC no more than 1 week prior to the initiation of treatment (enrollment 1 day prior to or on the day of treatment is strongly encouraged). Once the eligibility checklist is submitted a system-generated confirmation email will be sent to the enroller upon successful completion of the participant enrollment. If the on-line system is inaccessible, the site should notify the AMC ODMC (via email at [[contact]](mailto:[contact]) or via phone at [contact]) for further instructions.

## 5.0 TREATMENT PLAN

### 5.1 Agent Administration

Treatment will be administered on an outpatient basis. Reported adverse events and potential risks are described in [Section 7.0](#). Appropriate dose modifications are described in [Section 6.0](#). No investigational or commercial agents or therapies other than those described below may be administered with the intent to treat the participant's malignancy.

Cabozantinib will be administered orally as once daily doses continuously over 28 day cycles in each of three treatment strata in participant cohorts as detailed in the table below. The starting dose in each treatment Stratum will be Dose Level 1. Dose escalation will proceed in participant cohorts within each Stratum according to the scheme described in [Section 5.2](#).

**NOTES: The participant will be requested to maintain a medication diary of each dose of medication. The medication diary will be returned to clinic staff at the end of each course.**

**The site will be required to document study agent return by participant in source documents. Non-compliance with study agent administration should be noted at the time of diary collection and the participant should be instructed again regarding dosing instructions.**

**Missed cabozantinib doses will NOT be made up. Participants who have missed a dose should wait until the next scheduled dose to resume therapy.**

For Stratum A, one dose de-escalation cohort (Dose Level -1) will be permitted for excessive toxicity observed at the initial (Dose Level 1) cohort. For Stratum B and Stratum C, two dose de-escalation cohorts (up to Dose Level -2) will be permitted for toxicity observed at initial cohorts.

For participants treated on Stratum A no dose escalation will proceed beyond Dose Level 3 (60 mg). For participants treated on Stratum B, no dose escalation will proceed beyond Dose Level 2 (100 mg). For participants treated on Stratum C, no dose escalation will proceed beyond Dose Level 1.

Dose Escalation Schedule			
Dose Level	Dose of Cabozantinib (XL184)*		
	Stratum A ART Regimens Including Drugs that Inhibit CYP3A4 A (mg/day)	Stratum B ART Regimens Including Drugs that Induce CYP3A4 B (mg/day)	Stratum C All Other ART Regimens C (mg/day)
Level -2	-	20	20
Level -1	20 mg every other day	40	40
Level 1	20	60	60
Level 2	40	100	-
Level 3	60	-	-

*\* Cabozantinib (XL184) must be taken whole and on an empty stomach. Participants must fast for 2 hours before and 1 hour following each dose of cabozantinib (XL184). To permit pharmacokinetic sampling studies, AM dosing is required during the first cycle of therapy.*

AStratum A: Participants taking either ritonavir-boosted or cobicistat-boosted ART regimens

BStratum B: Participants taking either efavirenz or etravirine-based ART regimens.

CStratum C: Participants taking any antiretrovirals not specified in Stratum A or B as of November 30, 2012, and participants who are not taking an ART regimen.

**Note: if an antiretroviral is FDA-approved after November 30, 2012, consult the Study Pharmacologist for Stratum designation).**

#### 5.1.1 Cabozantinib (XL184)

Cabozantinib (XL184) must be taken whole and on an empty stomach. Participants must fast for 2 hours before and 1 hour following each dose of cabozantinib (XL184). **To permit pharmacokinetic sampling studies, AM dosing is required during the first cycle of therapy. Please refer to [Section 10.2](#) for additional information regarding required pharmacokinetic sampling in Cycle 1.**

#### 5.1.2 Other modalities or procedures

N/A

### 5.2 Definition of Dose-Limiting Toxicity

Dose escalation decisions for cabozantinib will be made after evaluation of toxicities in the first cycle of therapy. In this trial, a dose-limiting toxicity (DLT) will be defined as any cabozantinib-related grade 3 or 4 non-hematologic toxicity during the first cycle of therapy, including grade 3 nausea and/or vomiting and grade 3 diarrhea despite prophylaxis and/or treatment or any of the following grade 4 hematologic toxicities during the first cycle of therapy: thrombocytopenia and neutropenia of any duration (with or without fever or documented infection); additionally, treatment delay of greater than 7 days during Cycle 1 due to unresolved toxicity or any dose reduction required during Cycle 1 due to a cabozantinib-related adverse event (including for intolerable cabozantinib-related grade 2 non-hematological toxicity – per Table 6-1) will be considered a DLT.

For all participants who experience a DLT or other persistent and severe toxicity, a blood sample for pharmacokinetics analysis will be requested from the participant (if feasible). The samples should be drawn as close as possible to the time of the event.

If a DLT occurs in one participant at a particular dose level, up to 3 additional participants will be added to that cohort. If a second participant experiences a DLT, the maximally tolerated dose (MTD) of the study will have been exceeded. If 2 DLTs are experienced at the first cohort, one dose level de-escalation (Dose Level -1) will be permitted according to the study schema suggested in the treatment plan.

Management and dose modifications associated with the above adverse events are outlined in [Section 6.0](#).

Dose escalation will proceed in participant cohorts within each Stratum ([Section 5.1](#)) according to the following scheme. Participants are considered evaluable for the purpose of cohort dose escalations if in the first cycle they either experience a DLT (defined above), or receive at least 80% of the planned treatment dose and are followed for one full cycle without a DLT. Participants receiving less than 80% of the treatment dose during cycle 1 without a DLT may be replaced for the purpose of safety and PK evaluation at the discretion of the study team.

Number of Participants with DLT at a Given Dose Level	Escalation Decision Rule
0 out of 3	Enter 3 participants at the next dose level.
$\geq 2$	Dose escalation will be stopped. This dose level will be declared the maximally administered dose (highest dose administered). Three (3) additional participants will be entered at the next lowest dose level if only 3 participants were treated previously at that dose.
1 out of 3	Enter at least 3 more participants at this dose level. 
 
• If 0 of these 3 participants experience DLT, proceed to the next dose level.
 
• If 1 or more of this group suffer DLT, then dose escalation is stopped, and this dose is declared the maximally administered dose. Three (3) additional participants will be entered at the next lowest dose level if only 3 participants were treated previously at that dose.
 

$\leq 1$ out of 6 at highest dose level below the maximally administered dose	This is generally the maximally tolerated dose (MTD)/recommended phase II dose. At least 6 participants must be entered at the recommended phase II dose.

